5.5. Correlation Between Antiviral Effect and Clinical Course Endpoints

For each cohort separately, the relationship between primary antiviral effect endpoints and clinical course endpoints will be investigated.

Cohort 1

For antiviral effect endpoints:

- Log₁₀ RSV RNA viral load AUC_{Day 5}
- Time to confirmed undetectable RSV RNA viral load

For clinical course endpoints:

- PRESORS ObsRO summary parameters: key RSV symptoms and overall RSV symptoms:
 - Time (hours) to resolution (ObsRO): *24h supplementation free definition*
 - Change from Baseline in PRESORS ObsRO: key RSV symptoms and overall RSV symptoms at Day X, Day 8 and Day 10
 - Where Day X is defined as the day when at least 50% of Cohort 1 subjects, across all treatment groups, have been discharged from hospital.
- RSV-related complications (Yes vs No): modified definition
- RSV recovery scale (RRS) (ObsRO): Day 1 to Day 8
- Clinically resolved status (ClinRO): Day 1 to Day 8

- Time (hours) to hospital discharge from first dose of study drug
- Time (hours) to resolution of key RSV symptoms from hospital discharge
- Time to end of oxygen supplementation up to 72h from first hospital discharge
- Time to end of supplementation (oxygen and/or hydration/feeding) up to 72h from first hospital discharge

For each pair of variables (2 antiviral x 9 clinical course endpoints) and depending on data type (continuous vs categorical) the following will be used to explore the possible relationship:

- Spearman rank order correlation coefficients + scatterplots: evaluates the monotonic relationship between two continuous or ordinal variables. Ranges from -1 to 1 where 0 indicates no correlation.
- Box plots: graphically presents the association between continuous and binary variables.
- Kaplan-Meier survival curves: by binary category (if binary variable) or by quartiles of a continuous variable.
- Plot of \log_{10} RSV RNA viral load vs summary parameter: key RSV symptoms (ObsRO) (“worst hourly” [refer to [Table 6: Worst per Day](#) and : [Parameters based on PRESORS ObsRO](#)]) daily summary score over time.

Similarly, for outpatients (Cohort 2) but including, at a minimum, the relevant clinical course endpoints as described below.

Cohort 2

For antiviral effect endpoints:

- \log_{10} RSV RNA viral load AUC_{Day 5}
- Time to **confirmed undetectable** RSV RNA viral load

For clinical course endpoints, at a minimum the following will be explored:

- PRESORS ObsRO summary parameters: key RSV symptoms and overall RSV symptoms:
 - Time (hours) to resolution (ObsRO): *24h supplementation free definition*
 - Change from Baseline in PRESORS ObsRO: key RSV symptoms and overall RSV symptoms at Day X, Day 8 and Day 10
 - Where Day X is defined as the day when at least 50% of Cohort 1 subjects, across all treatment groups, have been discharged from hospital
- RSV-related complications (Yes vs No): modified definition

As new information becomes available, additional clinical course endpoints may be identified and explored utilizing the above methodology to ascertain possible relationships.

5.6. Decision Rules at Interim Analyses

During IAs, the primary viral load endpoint and 3 below-mentioned key clinical course endpoints are considered. Minimum acceptable value and target value for these key clinical course endpoints are defined in [Table 23](#):

Table 23: MAV and TV

Endpoint	Minimum Acceptable Value (MAV)	Target Value (TV)
Time to resolution of key RSV symptoms (ObsRO)	No difference (MAV = 0)	1 day (24 hours) reduction (TV = -1)
Change from baseline (CFB) in summary parameter: key RSV symptoms (ObsRO) at Day 8	No difference (MAV = 1)	20% larger change from baseline, where the change from baseline represents a reduction in score (TV = 1.2*)
Incidence of RSV-related Complication	No difference (MAV = 0)	10% absolute reduction in rate (TV = -0.1)

* This represents a 20% increase in the magnitude of the CFB and not in the summary parameter score itself (i.e. if the CFB in the Placebo treatment group is -1.0, then the target CFB for the active treatment group would be -1.2)

Note that the viral load endpoint will be evaluated on a combined dataset of both cohorts for each interim analysis, except for IA#1 where only Cohort 1 data are available. Clinical course endpoints will be evaluated in the community cohort only for IA#3 and IA#4.

For IA#3 and IA#4 analyses, in case of severe imbalance between ≤ 3 days and > 3 days since symptom onset and where there are more subjects in the > 3 to ≤ 5 days stratum than in the ≤ 3 days stratum (i.e. $> 55\%$ of subjects in the > 3 to ≤ 5 days stratum), a second analysis will be conducted considering 50% of subjects randomized in each stratum (symptom onset ≤ 3 days and symptom onset vs > 3 to ≤ 5 days) in each cohort separately. Chronological order of randomization (date and time) per stratum will be followed when defining the balanced dataset. In case there are inconsistencies in the results between the complete and the balanced analysis, no decision on altering the study (i.e. stopping for futility or enriching) will be taken and the study will proceed as planned and collect more data. In the case that a balanced analysis has been carried out (as described above), the sample size re-estimation at IA#3 will be performed on the balanced dataset only.

The IDMC will provide recommendations to the SC according to the below guidance:

Interim Analysis 1

The IDMC will review data on safety and tolerability, PK, and antiviral effect. Based on these data, the IDMC may make a recommendation to initiate enrollment in Cohort 2

Interim Analysis 2

The IDMC will consider stopping the study for futility if:

- The MCP-Mod trend test on viral load is non-significant at $\alpha=50\%$ (1-sided), based on combined data from Cohort 1 and Cohort 2

AND

- At least one of the following criteria is true:
 - 95% 2-sided confidence interval on the difference in median time to resolution of key RSV symptoms between the high dose and placebo group excludes effects as good as the TV (i.e. lower limit of the confidence interval is above TV of '-1 day'), based on combined data from Cohort 1 and Cohort 2

OR

- 95% 2-sided confidence interval on the difference in median time to resolution of key RSV symptoms between the high dose and placebo group excludes effects as good as the TV (i.e. lower limit of the confidence interval is above TV of ‘-1 day’), based on data from Cohort 1 only

The above rule is considered non-binding. If the above pre-defined futility rule is hit, the SC will review available viral load and clinical course data, and might ask to perform subgroup analysis including, but not limited to, onset of symptoms and age group. Based on this, the SC may also consider enriching the population (i.e. limit future enrollment to subjects with ≤ 3 days since symptom onset), if there is evidence that the drug is not providing benefit to the subjects whose symptoms onset is >3 days.

Interim analysis 3

The IDMC will consider enriching the population (i.e. limit future enrollment to subjects with ≤ 3 days since symptom onset), if

- At least 2 out of 4 endpoints have conditional power $<50\%$, where conditional power is defined as:
 - Viral load: conditional probability to reach success based on the MCP-Mod trend test at 1-sided alpha=2.5% at IA#4, based on combined data from Cohort 1 and Cohort 2.
 - Key clinical course endpoints: conditional probability of obtaining results in the “Go” region defined by a dual Go/No-Go framework at IA#4, based on data from Cohort 2 only.

The IDMC will review the re-calculation of the sample size using Cohort 2 data to limit the conditional probability of an inconclusive result to 20% on all clinical endpoints at the end of the study.

The IDMC will consider stopping the study for futility, if:

- The conditional power at IA#4 is $<50\%$ to demonstrate antiviral activity of JNJ-53718678 compared with placebo based on the MCP-Mod trend test on viral load at 1-sided alpha=2.5% based on combined data from Cohort 1 and Cohort 2.

AND

- 80% 2-sided confidence interval on at least 2 key clinical course endpoints excludes effects as good as the TV based on data from Cohort 2 only

AND

- None of the 80% 2-sided confidence intervals on any key clinical course endpoint excludes effects as bad as the MAV based on data from Cohort 2 only

For viral load, the conditional probability of success at IA#4 using combined data from Cohorts 1 and 2 will be calculated assuming i) no enrichment and ii) enrichment as described below.

In both cases, the conditional probability of success will be set to 1 if the 1-sided p-value for the MCP-Mod trend test is less than 2.5% at IA#3, as success has already been reached. Otherwise, the conditional Type I error will be calculated using the inverse-normal combination approach:

$$\rho = 1 - \Phi \left(\frac{\Phi^{-1}(0.975) - \sqrt{w_1} \Phi^{-1}(1 - p_{Full})}{\sqrt{1 - w_1}} \right)$$

where:

- p_{Full} represents the 1-sided p-value for the MCP-Mod trend test for the full population at IA#3
- $w_1 = n_1 / n$
- n_1 represents the total number of randomized patients in Cohorts 1 and 2 at the time of IA#3
- $n = 294$, the planned total number of randomized patients in Cohorts 1 and 2 at IA#4

Given the conditional Type I error, the critical value for the MCP-Mod test based on new data from IA#4 only will be calculated. The conditional probability of success at IA#4 will be calculated under the observed test statistic at IA#3 (Z_1), adjusted for the sample size of the new data at IA#4 as:

$$CP_x = 1 - P(\bigcap_{i=1}^3 \{Z_{i,2} \in (-\infty, CRV)\})$$

where:

$$Z_2 \sim N \left(\mu_{Z,2} = \sqrt{\frac{n_2}{n_{1,x}}} Z_{1,x}, corr = corr_{MCPx} \right)$$

and:

- x corresponds to the decision not to enrich / to enrich at IA#3
- $Z_{1,x}$ represents the vector of observed MCP-Mod test statistics at IA#3 (Linear, Emax and Exponential models) based on the population of interest (full population for no enrichment and the sub-population with symptom onset ≤ 3 days for enrichment).
- Z_2 represents the vector of observed MCP-Mod test statistics for the second stage.
- $Z_{i,2}$ represents the observed MCP-Mod test statistic for the second stage (based on the new data at IA#4) for model i.
- $\mu_{Z,2}$ represents the vector of mean MCP-Mod test statistics for the second stage, which is estimated using the observed test statistics at IA#3.

- $n_{1,x}$ represents the number of randomized patients in Cohorts 1 and 2 at the time of IA#3 for the population of interest (full population for no enrichment and sub population for enrichment).
- n_2 represents the number of additional patients to be included in Cohorts 1 and 2 up until IA#4 (i.e. 294 - $n_{1,Full}$, where 294 is the total number of randomized subjects in Cohorts 1 and 2 at IA#4).
- $corr_{MCPx}$ _represents the correlation matrix of the test statistics at IA#3 for the population of interest.
- CRV describes the critical value at IA#4, which is calculated based on the conditional 1-sided Type I error ρ , taking the multiplicity adjustment for MCP-Mod into account.

For the key clinical course endpoints, the conditional probabilities of obtaining results in the “Go”, “Stop” and “Consider” regions at IA#4 and at the end of the study will be evaluated for Cohort 2 assuming i) no enrichment and ii) enrichment. Calculations of conditional power at IA#4 will assume a total sample size of 150 for Cohort 2 and calculations of conditional power at the end of the study will be calculated assuming total sample sizes for Cohort 2 of 150, 180, 210, 240, 270 and 300.

Analyses will be conducted as described below for each of the three key clinical course endpoints in order to estimate the following p-values at IA#3:

- $p_{Full;TV}$ and $p_{Sub;TV}$: 1-sided p-values to test the null hypothesis that the difference between the high dose and the placebo group is at least as good as the target value (TV) for the full and sub-populations against the alternative hypothesis that the difference between the high dose and the placebo group is worse than the TV.
- $p_{Full;MAV}$ and $p_{Sub;MAV}$: 1-sided p-values to test the null hypothesis that the difference between the high dose and the placebo group is no better than the minimum accepted value (MAV) for the full and sub-populations against the alternative hypothesis that the difference between the high dose and the placebo group is better than the MAV.

Time to resolution of key RSV symptoms

- The time to resolution of key RSV symptoms will be analyzed using an accelerated failure time (AFT) model, using the log-logistic distribution as described in Section 5.3.2.2. However, the term for baseline \log_{10} viral load will be retained whether or not it is significant at the 10% significance level. The median time to resolution for the placebo group (T_p) in days will be estimated based upon this model and the TV that corresponds to a 1-day reduction for the high dose group will be calculated as a log relative reduction (i.e. as $\log[(T_p-1)/T_p]$). The MAV of no difference corresponds to a log relative reduction of $\log(T_p/T_p) = 0$. The 1-sided p-values for the tests to compare the difference between the high dose and placebo groups versus the TV and MAV will be derived using normal approximations for appropriate contrasts, Z_{TV} and Z_{MAV} .

Change from baseline in key RSV symptoms at Day 8

- The change from baseline in key RSV symptoms at Day 8 will be analyzed using a restricted maximum likelihood repeated measures approach as described in Section

5.3.2.2. The adjusted mean reduction from baseline for the placebo group will be estimated based upon this model (\bar{x}_P) and the TV that corresponds to a 20% larger change from baseline for the high dose group (i.e. $1.2\bar{x}_P$) will be calculated. The MAV corresponds to a difference in the change from baseline of 0 (i.e. $1.0\bar{x}_P$). The 1-sided p-values for the tests to compare the difference between the high dose and placebo groups versus the TV and MAV will be derived using normal approximations for appropriate contrasts, Z_{TV} and Z_{MAV} .

Incidence of RSV-related complications

- The 1-sided p-values to compare the proportion of subjects with at least one RSV-related complication between the high dose and placebo groups versus the MAV and TV will be derived using a normal approximation to the binomial distribution; where:

$$\hat{p}_1 - \hat{p}_2 \sim N \left(p_1 - p_2, \frac{p_1(1-p_1)}{n_1} + \frac{p_2(1-p_2)}{n_2} \right)$$

The TV of an absolute reduction in rate of 10% corresponds to a difference in the proportion of subjects with at least one RSV-related complication in high dose versus placebo of -0.1. The MAV corresponds to a difference in the proportions of 0.

For each of the three clinical course endpoints, the conditional probability for the Stop decision for the situation without/with enrichment and for each assumed total sample size will be calculated as:

- $CP_{x;Stop} = 1 - \Phi \left(\frac{\Phi^{-1}(0.9) - \sqrt{w_1} \Phi^{-1}(1-p_{Full;TV})}{\sqrt{1-w_1}} - \sqrt{\frac{n_2}{n_{1,x}}} \Phi^{-1}(1-p_{x;TV}) \right)$

The conditional probability for the Go decision for the time to resolution of key RSV symptoms and the incidence of RSV-related complications will be calculated as:

- $CP_{x;Go} = \Phi \left(\min \{ CRV_{TV} - \mu_{x;TV}, \mu_{x;MAV} - CRV_{MAV} \} \right)$

where:

- $CRV_{TV} = \frac{\Phi^{-1}(0.9) - \sqrt{w_1} \Phi^{-1}(1-p_{Full;TV})}{\sqrt{1-w_1}}$ and $CRV_{MAV} = \frac{\Phi^{-1}(0.9) - \sqrt{w_1} \Phi^{-1}(1-p_{Full;MAV})}{\sqrt{1-w_1}}$
- $\mu_{x;TV} = \sqrt{\frac{n_2}{n_{1,x}}} \Phi^{-1}(1-p_{x;TV})$ and $\mu_{x;MAV} = \sqrt{\frac{n_2}{n_{1,x}}} \Phi^{-1}(1-p_{x;MAV})$
- x corresponds to the decision not to enrich / to enrich at #IA3
- $p_{x;TV}$ and $p_{x;MAV}$ represents p-values for the population of interest (full population for no enrichment and sub population for enrichment).
- $n_{1,x}$ represents the number of randomized patients in Cohort 2 at the time of IA#3 for the population of interest.

- n_2 represents the number of additional patients to be included in Cohort 2 up until the end of the study (i.e. $N - n_{1,Full}$, where N represents the total number of randomized subjects in Cohort 2 at the end of the study).
- $w_1 = n_1 / n_{Primary}$ where $n_{Primary} = 225$ is defined as midway between the planned sample size ($N=150$) and the maximum sample size ($N=300$) for Cohort 2.

The conditional probability of the Go decision for the change from baseline in key RSV symptoms at Day 8 needs to take the correlation, ρ , of Z_{TV} and Z_{MAV} into account.

$$\rho = -\frac{\left(\frac{1}{n_{H1,x}} + TV * MAV \frac{1}{n_{P1,x}}\right)}{\left(\sqrt{\frac{1}{n_{H1,x}} + TV^2/n_{P1,x}}\right)\left(\sqrt{\frac{1}{n_{H1,x}} + MAV^2/n_{P1,x}}\right)}$$

The conditional probability of the Go decision is calculated using a bivariate normal distribution where:

- $CP_{x;Go} = P(Z_{x2;TV} < CRV_{TV} \cap Z_{x2;MAV} > CRV_{MAV}; \mu = (\mu_{x;TV}, \mu_{x;MAV}), \rho)$

Where:

- $n_{H1,x}$ represents the number of Cohort 2 subjects in the high dose group that were included in the analysis at IA#3 for the population of interest.
- $n_{P1,x}$ represents the number of Cohort 2 subjects in the placebo treatment group that were included in the analysis at IA#3 for the population of interest.
- $Z_{x2;TV}$ represents the test statistic to test the null hypothesis that the difference between the high dose and the placebo treatment group is at least as good as the target value (TV) at the end of the study (full population for no enrichment and sub population with symptom onset ≤ 3 days for enrichment).
- $Z_{x2;MAV}$ represents the test statistic to test the null hypothesis that the difference between the high dose and the placebo treatment group is no better than the minimum acceptable value (MAV) at the end of the study (full population for no enrichment and sub population with symptom onset ≤ 3 days for enrichment).

For all clinical course endpoints, the conditional probability of an inconclusive result will then be calculated as:

$$CP_{x;Inconclusive} = 1 - CP_{x;Stop} - CP_{x;Go}$$

Interim analysis 4

The IDMC will consider stopping the study for futility, if:

- Viral load did not meet success based on the MCP-Mod trend test at 1-sided alpha=2.5% based on combined data from Cohort 1 and Cohort 2

AND

- 80% 2-sided confidence interval on at least 2 key clinical course endpoints excludes effects as good as the TV based on data from Cohort 2 only

AND

[figure not shown]
- None of the 80% 2-sided confidence intervals on any key clinical course endpoints excludes effects as bad as the MAV based on data from Cohort 2 only

For IA#3 and IA#4 two separate tests for two study populations are conducted and no formal multiplicity adjustments for the multiple study populations were implemented.

- Test for full population
- Test for subpopulation of patients ≤ 3 days since symptom onset

The futility rules defined are applied to each population separately. For decision-making, results of both populations will be considered. The following figure (refer to [Figure 3: Decision Flowchart](#)) provides an overview of the decision rules based on different endpoints to determine whether to stop the study for futility. Study will be stopped for futility if futility is reached in both populations.

Figure 3: Decision Flowchart

TV- Target value; MAV -Minimum Acceptable Value

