1.4. Sample Size Justification

The basis of the sample size calculation are the antiviral activity data of Study 53718678RSV1005. In that study, the mean difference in RSV viral load AUC from baseline until Day 5 of the placebo group versus active (adjusted for baseline viral load) was estimated as 105 \log_{10} copies.hour/mL (corresponding to a 25% reduction) and the standard deviation (SD) on the RSV viral load AUC as 85 \log_{10} copies.hour/mL (corresponding to a coefficient of variation [CV] of approximately 20%).

Assuming a more conservative reduction in RSV viral load AUC of 20% compared to placebo, considering a CV of 35% (slightly higher variability than observed in Study 53718678RSV1005), and a 1-sided alpha of 2.5%; the power to conclude a dose-response using the Multiple Comparison Procedure-Modeling (MCP-Mod) procedure under different assumptions for the dose-response relationship (linear, E_{max} and exponential) is provided in [Table 1](#). Based on Study 53718678RSV1005 results, no discrimination between the proposed doses is expected (i.e. E_{max} dose-response shape was observed).

Table 1: Power (%) to Conclude Dose-response Using MCP-Mod Under Different Assumptions for the Dose-response Relationship

Assumed CV	Assumed dose-response relationship		
	Linear	E_{max}	Exponential
Cohort 1 + Cohort 2 (N=74 per treatment arm)			
20%	100.0	100.0	100.0
35%	92.3	95.3	96.6
Cohort 2 only (N=50 per treatment arm)			
20%	99.8	100.0	100.0
35%	79.0	84.0	86.9
Cohort 1 only (N=24 per treatment arm)			
20%	91.5	94.7	96.2
35%	47.1	51.2	54.7

If data of both cohorts are combined (N=74 per treatment arm), the power to conclude dose-response is more than 90% for all 3 different assumptions for the dose-response relationship. If data from Cohort 1 cannot be combined with data from Cohort 2 (e.g. due to inconsistency [means and/or variability] in viral load data between cohorts per treatment group), the power to conclude a dose-response using the MCP-Mod procedure in Cohort 2 (N=50 per treatment arm) is at least 79%.

The sample size in Cohort 1 only ($n \geq 24$ per treatment arm) will provide sufficient power (approximately 90%) if the reduction in RSV viral load AUC is at least 20% with a CV which is not higher than observed in Study 53718678RSV1005 (i.e. 20%).

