5.1.1. Level of Significance

The primary objective is to establish antiviral activity of JNJ-53718678. The primary efficacy endpoint is the RSV RNA viral load AUC from immediately prior to first dose of study drug through Day 5 ($AUC_{Day\ 5}$) derived from the RSV RNA viral load as measured by a qRT-PCR assay in nasal swabs. A hybrid methodology that combines aspects of multiple testing with modeling techniques (MCP-Mod) will be used for evaluating dose-

response trends and estimating the dose-response relationships. The dose-response will be tested at each (interim) analysis at alpha=2.5% (1-sided).

The primary analysis will only adjust for multiplicity with respect to the candidate models included into the MCP-Mod test. Due to the exploratory nature of the study, no adjustment for multiplicity due to sub-populations and adaptations will be considered in the primary analysis. A secondary analysis approach will be performed to control for multiplicity in the clinical course endpoints and for adaptations (see Section [5.2.3.2](#)).

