5.2.3. Analysis Method

Mean \log_{10} RSV RNA viral load values over time will be analyzed using a restricted maximum likelihood based repeated measures approach (MMRM). The analysis model includes fixed (discrete) effect parameters for treatment, randomization stratification factors (derived), analysis visit and treatment-by-analysis visit interaction, as well as continuous covariates for baseline \log_{10} viral load and baseline \log_{10} viral load-by-analysis visit interaction. An unstructured (co)variance structure will be used to model the within-subject errors. In case this model will not converge, the Toeplitz covariance structure will be applied. The Kenward-Roger approximation will be used to estimate the denominator degrees of freedom.

For subgroup analyses, the model will also include the subgroup variable as a covariate and the subgroup-by-treatment, subgroup-by-analysis visit and subgroup-by-analysis visit-by-treatment interactions. For details about subgroups please see Section 2.4.

A generalized MCP-Mod (1) approach at 1-sided alpha-level of 2.5% will be applied based on the estimated AUC treatment group effect and variance covariance matrix. Candidate models are given by the EMax (0.40428), Exponential (0.36411) and Linear model, with the aim to test for existence of drug-related effects. Each of the dose-response shapes in the candidate set will be tested using the corresponding contrast t-test statistic, employing a critical value derived for the maximum of the t-test statistics (based on the associated multivariate t-distribution) to ensure appropriate multiplicity correction that preserves a 1-sided 0.025 Type I error rate. A dose-response trend is established when the maximum of the t-test statistics exceeds the critical value.

MCP-Mod uses dose levels 0, 3 and 9 mg/kg which correspond to Placebo, Low and High dose respectively according to the dose/kg for age-group 3 as described in Section 1.2.

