Let the cumulative sample sizes for Cohort i up to analysis j be defined as n_{ij} :

	IA#1	IA#2	IA#3	IA#4	Final Analysis
Cohort 1 (n=144)	n_{11} (~36)	n_{12} (~75)	n_{13} (~144)	n_{14} (~144)	n_{15} (~144)
Cohort 2 (n=150)		n_{22} (~36)	n_{23} (~75)	n_{24} (~150)	n_{25} (~300)

RSV RNA Viral Load:

The total sample size planned for the primary analysis on viral load is given as: $n_{\text{Primary}}=294$. This constitutes the sample size of both Cohorts 1 and 2.

Stagewise weights and 1-sided p-values are defined as:

	IA#2	IA#3	IA#4
No enrichment:			
Weight	1		
p-value	p_{14}^F		
Final p-value (global)	p_{14}^F		
Final p-value (sub)	p_{14}^S		
Enrich at IA#2:			
Weight (w_{ij})	$(n_{12}+n_{22})/n_{\text{Primary}}$	$(n_{\text{Primary}} - n_{12} - n_{22})/n_{\text{Primary}}$	
p-value	p_{12}^F	p_{34}^S	
Final p-value (global)	$1 - \Phi \left(\sqrt{w_{12}} \Phi^{-1}(1 - p_{12}^F) + \sqrt{w_{34}} \Phi^{-1}(1 - p_{34}^S) \right)$		

	IA#2	IA#3	IA#4
Final p-value (sub)	$1 - \Phi \left(\sqrt{w_{12}} \Phi^{-1}(1 - p_{12}^S) + \sqrt{w_{34}} \Phi^{-1}(1 - p_{34}^S) \right)$		
Enrich at IA#3:			
Weight (w_{ij})	$(n_{13}+n_{23})/n_{Primary}$	$(n_{Primary}-n_{13}-n_{23})/n_{Primary}$	
p-value	p_{13}^F	p_{44}^S	
Final p-value (global)		$1 - \Phi \left(\sqrt{w_{13}} \Phi^{-1}(1 - p_{13}^F) + \sqrt{w_{44}} \Phi^{-1}(1 - p_{44}^S) \right)$	
Final p-value (sub)		$1 - \Phi \left(\sqrt{w_{13}} \Phi^{-1}(1 - p_{13}^S) + \sqrt{w_{44}} \Phi^{-1}(1 - p_{44}^S) \right)$	

- p_{ij}^F defines the p-value for the MCP-Mod test for data collected from in stages i to j in the full population
- p_{ij}^S defines the p-value for the MCP-Mod test for data collected from in stages i to j in the sub population

A p-value combination for the test of the sub-population is required, as the enrichment decision implies a sample size re-calculation for the sub-population.

Clinical Course Endpoints:

Sample size for clinical course endpoints is only based on Cohort 2. Let $n_{Primary} = 225$ be defined as midway between planned ($N= 150$) and maximum sample size ($N=300$).

	IA#2	IA#3	IA#4	Final Analysis
No enrichment:				
Weight (w_{ij})	$(n_{23})/n_{Primary}$		$(n_{Primary}-n_{23})/n_{Primary}$	
p-value	p_{23}^F		p_{45}^F	
Final p-value (global)	$1 - \Phi \left(\sqrt{w_{23}} \Phi^{-1}(1 - p_{23}^F) + \sqrt{w_{45}} \Phi^{-1}(1 - p_{45}^F) \right)$			

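### At IA#3 the viral-load conditional power for continuing without enrichment is computed for a stage-wise combination test, although the SAP's test in that case is one pooled MCP-Mod test: wrong as written, low priority

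*SAP*

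**What the plan says.** Section 5.6, Interim analysis 3, defines viral-load conditional power as the "conditional probability to reach success based on the MCP-Mod trend test at 1-sided alpha=2.5% at IA#4", on combined data from both cohorts. A value below 50% is one of four endpoint votes for enrichment (two are needed) and the first of three joint conditions for futility. The futility rule at Interim analysis 4 judges viral-load success by the same test on combined data.

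The test itself is fixed in Section 5.2.3.2. In the viral-load table, the no-enrichment row has weight 1 and final p-value p_14^F, where p_ij^F "defines the p-value for the MCP-Mod test for data collected from in stages i to j in the full population". Inverse-normal combinations appear only in the rows for enrichment at IA#2 or IA#3. Section 5.1.1 adds that "no adjustment for multiplicity due to sub-populations and adaptations will be considered in the primary analysis". So both the primary analysis and the secondary, adaptation-controlling approach use one pooled test when there is no enrichment.

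The conditional-power algorithm in Section 5.6 has two branches, and each covers both options:
- If the IA#3 MCP-Mod p-value is below 2.5%, conditional power is set to 1.
- "Otherwise, the conditional Type I error will be calculated using the inverse-normal combination approach". The conditional error comes from the multiplicity-adjusted full-population p-value. A new MCP-Mod critical value (CRV), again adjusted for three models, is then applied to the second-stage statistics only.

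**The concern.** With one contrast, the inverse-normal combination and the pooled test are the same test. With the maximum of three correlated contrasts they are not. The combination reduces the stage-1 vector to one adjusted p-value and then sets one common hurdle for all three second-stage contrasts. The pooled test gives each contrast its own remaining hurdle, which depends on its own stage-1 value. The contrast that led at stage 1, which also has the largest assumed drift, has the lowest remaining hurdle in the pooled test.

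The SAP thus reports to the IDMC, as the chance of success at IA#4 without enrichment, a probability that belongs to a different test. Viral load is the primary endpoint and the figure is compared with a fixed 50% line, so a directional error could push a borderline result towards restricting or stopping the study. For the enrichment option the combination formula does match Section 5.2.3.2, so the mismatch affects only one of the two options.

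**Working it through.** **Inputs.** One-sided 2.5% (Section 5.1.1); "Candidate models are given by the EMax (0.40428), Exponential (0.36411) and Linear model" and "MCP-Mod uses dose levels 0, 3 and 9 mg/kg" (Section 5.2.3); 20% reduction with CV 35%, that is 0.20/0.35 = 0.571 SD (Section 1.4); about 144 + 75 = 219 subjects at IA#3 (Section 5.2.3.2) of 294 at IA#4 (Section 5.6). Hence w1 = 219/294 = 0.745, sqrt(w1) = 0.863, sqrt(1-w1) = 0.505, n2 = 75 and sqrt(n2/n1) = 0.585.

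**Reproducing Table 1 first.** Optimal contrasts for doses 0/3/9 with equal arms reproduce the stated power at CV 35% (linear / Emax / exponential):
- N=74: 92.4/95.3/96.6 against 92.3/95.3/96.6 in the SAP.
- N=50: 79.0/84.0/86.9, as in the SAP.
- N=24: 47.0/51.1/54.5 against 47.1/51.2/54.7.

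The contrasts are therefore the SAP's own. Their correlations are 0.80 (linear with Emax), 0.94 (linear with exponential) and 0.56 (Emax with exponential). The large-sample critical value of the maximum is c = 2.23.

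**Formulas compared**, both with drift sqrt(n2/n1)*Z1:
- SAP: rho = 1 - Phi[(1.960 - sqrt(w1)*Phi^-1(1-p))/sqrt(1-w1)]; CRV is the MCP-Mod critical value at level rho; CP = P(max_i Z2,i > CRV).
- Pooled test: CP = P(max_i{sqrt(w1)*Z1,i + sqrt(1-w1)*Z2,i} > c).

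**One contrast.** The normal score equals Z1, so the hurdles are identical. At Z1 = 1.8 both give 0.598.

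**Three contrasts, worked case.** Let the observed pattern be Emax with maximum 1.95, so Z1 is 1.95 (Emax), 0.80 x 1.95 = 1.56 (linear) and 0.56 x 1.95 = 1.09 (exponential).
- SAP: adjusted p = 0.048, normal score 1.668; (1.960 - 0.863 x 1.668)/0.505 = 1.03, so rho = 0.152 and CRV = 1.34 for every contrast. CP = 49.5%.
- Pooled: the Emax hurdle is (2.23 - 0.863 x 1.95)/0.505 = 1.08; the linear and exponential hurdles, by the same formula, are 1.75 and 2.55. CP = 53.3%.

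Other points at the same sample size:

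| Observed shape, maximum Z | SAP formula | Pooled test |
|---|---|---|
| Linear, 1.90 | 47.5% | 50.6% |
| Emax, 1.90 | 44.8% | 48.8% |
| Exponential, 1.90 | 44.9% | 49.7% |
| Exponential, 1.95 | 49.5% | 54.2% |
| Linear, 2.00 | 56.4% | 59.7% |
| Emax, 2.00 | 53.8% | 57.9% |
| Exponential, 2.00 | 54.2% | 58.4% |

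These are accurate to a few tenths of a point. Conditional power reaches 50% at an IA#3 p-value of about 0.047 by the SAP formula and about 0.051 for the pooled test.

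**Over all IA#3 results with p of 2.5% or more.** The SAP value never exceeded the pooled value. The largest gap was about 10 points at n1 = 219 and about 9 points at n1 = 155. The latter is an assumed smaller look, equal to the 115 + 40 subjects in the interim cut cited in Section 5.3.1.2.1. For true reductions of 0 to 20% with CV 35%, the SAP value was below 50% while the pooled value was at or above 50% in 0.3 to 2.5% of results (n1 = 219) or 0.6 to 3.1% (n1 = 155). No reverse flip was found.

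**Override.** For IA#3 p between 0.015 and 0.025, pooled-test conditional power is 0.76 to 0.89 at n1 = 219 (0.89 to 0.96 at n1 = 155), against the assigned value of 1.

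**The case against.** Three stronger readings are tempting, and the documents do not support them.

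- A reader might infer that the SAP's conditional power is always too low. It is not. The override replaces the formula by 1 when IA#3 p is below 2.5%, and that is above the pooled-test value by up to about 24 points (1 - 0.76). The understatement holds only where the formula applies.
- A reader might infer that the formula stands for a stricter test. Combining two valid adjusted p-values by inverse-normal weights is itself a 2.5% test; simulation under no effect gave 2.5% for both. At 0.286 SD (a 10% reduction with CV 35%), unconditional power, pooled against combination, is 49.4% against 49.1% (linear), 53.7% against 52.3% (Emax) and 57.3% against 55.7% (exponential). In 2 to 3% of trials at that effect the combination rejects when the pooled test does not. The conditional gap arises because the drift is set to the observed Z1, which favours the pooled test. Nor is the stage-1 pattern wholly lost, since the drift uses the full vector.
- A reader might infer that the trial would often be enriched or stopped wrongly. Enrichment needs a second endpoint below 50%. Futility also needs both clinical confidence-interval conditions and must be met in both populations. The IDMC only considers either action, and the Sponsor Committee decides.

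It is also fair that conditional power at the observed effect is noisy: at 0.286 SD its interquartile range was about 0.12 to 0.96, so 3 to 5 points is small beside it. Type I error, the primary test and the final estimate are untouched. All of this bears on priority. None of it makes the no-enrichment figure the probability that Section 5.6 says it is.

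**Conclusion.** The SAP contradicts itself on which IA#4 test the no-enrichment conditional power refers to, and the formula follows the wrong one. Where the formula applies, the understatement is typically 3 to 5 points near the 50% line along the candidate shapes and at most about 10. The viral-load criterion is misplaced below 50% in roughly 0.3 to 3% of IA#3 results, and the reverse was not found. The override is a second mismatch in the same paragraph, but pooled conditional power is already well above 50% there, so it does not move the decision. The effect on a final recommendation has not been quantified and must be smaller than these rates.

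Assumptions: normal approximation with known variance, equal arms, information proportional to the number randomised, the same contrast correlations at both stages, and candidate parameters on the mg/kg scale (the scale that reproduces Table 1). Rescaling doses to 0-1 does not reproduce Table 1; it gives the same direction with gaps of at most about 6 to 7 points. Section 5.6 does not name which option's conditional power enters the 50% rules; I read it as the no-enrichment value.

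Label: wrong as written; low priority.

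**What to change.** In Section 5.6, Interim analysis 3:
- For no enrichment, replace the combination step by CP = P(max_i{sqrt(w1)*Z1,i + sqrt(1-w1)*Z2,i} > c), with c the one-sided 2.5% MCP-Mod critical value of the pooled test and Z2 ~ N(sqrt(n2/n1)*Z1, corr_MCP).
- Keep the inverse-normal formula for the enrichment option only, where it agrees with Section 5.2.3.2.
- State whether the override for p below 2.5% means that success is declared at IA#3. If success is judged at IA#4, drop the override for no enrichment and apply the pooled formula there too; otherwise the value jumps from about 0.77 to 1 at p = 0.025.

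The new formula remains an approximation for an MMRM-derived AUC in the ITT-i set, and one sentence should say so. The cost is a short wording change and a few lines of code, with no effect on data collection or patients.
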